9. RESEARCH METHODS

9.1. Study Design

This study will assess a retrospective cohort of users of Mysimba/Contrave with up to 548 days (~18 months) after initiation with treatment with Mysimba/Contrave. This study will describe Mysimba/Contrave utilisation and incidence of AESIs for users compliant and non-compliant with the SmPC.

Preliminary feasibility of databases throughout Europe has been conducted annually in advance of study start. EHR and administrative health databases were assessed in the following countries:

1.	Austria	11.	Hungary	21.	Slovenia
2.	Bulgaria	12.	Ireland	22.	Spain
3.	Croatia	13.	Italy	23.	Sweden
4.	Cyprus	14.	Latvia	24.	United Kingdom
5.	Czech Republic	15.	Lithuania	25.	EU-wide IQVIA
6.	Denmark	16.	Norway		administrative
7.	Estonia	17.	Poland		health data
8.	Finland	18.	Portugal		platform
9.	Germany	19.	Romania		
10.	Greece	20.	Slovakia		

The sales and estimated number of patients available in databases have been provided to PRAC. After extensive feasibility assessment, several databases for this study have been identified and accordingly selected based on the number of Mysimba prescriptions and availability of a suitable database in each country:

- 1. Denmark (Danish National Health Registries) Mysimba not reimbursed
- 2. Finland (Finnish National Registries) Mysimba reimbursed but restricted to morbidly obese
- 3. Norway (Norwegian Health Registries) Mysimba reimbursed but restricted to morbidly obese
- 4. Sweden (National Board of Health and Welfare) Mysimba not reimbursed

These countries make use of record linkage systems where patient level data are matched by cross-referencing de-identified (US) or pseudanomynized (Nordic, Laugersen et al., 2021) data through a unique personal identification number between different registers of interest managed by the respective data controllers in a manner that complies with Regulation 2016/679 or the EU General Data Protection Regulation.

As noted in Mysimba PBRER_10 (dated 10 NOV 2022), no new study countries have been identified since EMA endorsement of the NB-451 study protocol dated 15 NOV 2022. As such, the NB-451 study is not expected to be conducted in additional EU countries, given the need for at least 548 days of availability in the data after the index date of Mysimba first use, and now that the NB-451 study is underway and anticipated to finish by December 2025.

Data from the U.S., which remains the principal geographical region of Contrave sales and utilization, will be included in this study as well as data sources across Europe meeting the feasibility requirements. The study will be completed when final analyses are completed for all databases in which data collection was initiated.

9.1.1. Inclusion Criteria

Patients will be included in the study if they meet the following inclusion criteria:

- 1. At least one prescription of Mysimba/Contrave in his/her medical records any time during the study period (US) OR at least one dispensing of Mysimba/Contrave in his/her registry any time during the study period (Nordic);
- 2. At least 365 days of computerized records prior to first Mysimba/Contrave prescription or dispensing date; and 3Patient is active (i.e., alive and registered/accruing data) at the time of the first Mysimba/Contrave prescription or dispensing date.

9.1.2. Exclusion Criteria

All patients meeting inclusion criteria will be included in the study; no exclusion criteria will be applied.

9.2. Setting

The study cohort will consist of all users of Mysimba/Contrave with at least 365 days of database data (baseline period) before the date of first prescription or dispensing of Mysimba/Contrave, as

applicable per database (i.e., index date). All available follow-up data up to 548 days after the index date will be included for each patient.

[figure not shown]
9.3. Variables

9.3.1. Exposure

Exposure to Mysimba/Contrave will be identified through medication prescription or dispensing data (i.e., prescription or dispensing date, dosage [where available], and duration [where available]). The first Mysimba/Contrave prescription after 365 days with no prescription will be the index date, as depicted in Figure 1. All prescriptions of Mysimba/Contrave (or the two component products dispensed within 15 days) during the 548 days (18 months) following the index date will be captured. Patients will be assessed during the entire 548 days following the index date.

Figure 1. Index date, Exclusion and Covariate Assessment, and Follow-up Time for Study

Index Date (First prescription of Mysimba) Day 0

- a. Data are 'acceptable for research' for the patient and practice, coverage with computerized records throughout time period with no gaps
- b. Baseline conditions included: BMI, height, most recent weight, weight-related comorbidities (e.g., diabetes, dyslipidaemia), neuropsychiatric conditions (mania, bipolar disorder, major depressive disorder [MDD], anorexia nervosa, bulimia), hypertension, end-stage renal disease, seizure disorder, hepatic impairment (defined by Child-Pugh score category), central nervous system tumour, substance use/abuse including acute opiate withdrawal,;uncontrolled hypertension, seizures, bipolar disorder, MDD, anorexia nervosa, or bulimia; use of: naltrexone, bupropion, opioid or opiate agonist, or MAOI; pregnancy, or breastfeeding
- c. Earliest of: death, disenrollment, 548 days of follow-up, end of the study period

9.3.1.1. Duration of Mysimba/Contrave Use

Duration of Mysimba/Contrave use will be determined based on prescription or dispensing data (depending on availability in the data source). The days' supply for each prescription will be used to determine the days of medication covered by that prescription. If days' supply is unavailable for a prescription or dispensing, it will be imputed as the mode for the most granular medication variable level available (e.g., by National Drug Code [NDC] in U.S. data, ATC in Nordic data) for the database. The count of duration (days) will include all days during which medication was available without accounting for overlap (i.e., no stockpiling will be included in the duration), a gap of up to half of the days' supply of the immediately preceding prescription, and a wash-out after the end of the last prescription days' supply (Figure 2). After the initial episode of Mysimba/Contrave duration, the duration of any subsequent episodes will also be captured.

[figure not shown]
Duration will be assessed in two ways:

- 1. Continuous treatment in the initial Contrave duration: the number of days duration in the initial Contrave episode (two continuous treatment episodes are in Figure 2; the first is 106 days and the second is 45 days [225-180 days])
- 2. Total duration of Mysimba/Contrave: the number of days duration in the 548 days (18 months) after the index Mysimba/Contrave prescription (the total duration of Mysimba/Contrave use in Figure 2 is 106+45 =151 days)

For Mysimba, similar calculations will be done, except that the day's supply will be 28-days after titration.

[figure not shown]
Figure 2. Duration of Mysimba/Contrave Use Episodes

U.S. Contrave

accounted for in the analysis

Nordic Countries

initial prescription or dispensing is 38 ½ day supply which includes 28 days for titration. Each dispensing is 112 pill count. Stockpiling will not be accounted for in the analysis

In addition, the number of prescriptions, number and duration of treatment episodes and duration between treatment episodes will be described.

9.3.1.2. Dosage of Mysimba/Contrave Use

When available, the listed dose of Mysimba/Contrave within each prescription or dispensing will be used as the dose for that patient. However, dose is unlikely to be available in Nordic data and sporadically available in US data. When dose is not provided, then an assumption of the standard dosing (4 pills per day with 32mg naltrexone and 90 mg bupropion in each pill) will be used as the dose for primary analyses. Sensitivity analyses will assign alternate dosing for specific patient groups (see section 9.7.2).

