DRUG UTILISATION AND SAFETY STUDY OF MYSIMBA/CONTRAVE IN EUROPE AND THE UNITED STATES

Protocol Number: NB-451 Version: Draft 4.0

Sponsor: Currax Pharmaceuticals LLC*

[name],

[name]

[name] [contact]

[contact]

This submission contains CONFIDENTIAL material and information and should be restricted in its distribution. Do not copy without the permission of the Sponsor.

* Orexigen Therapeutics Ireland Limited (OTIL, based in Dublin Ireland EU) is the Marketing Authorization Holder (MAH) for Mysimba[®]/Contrave[®] (naltrexone HCl/ bupropion HCl prolonged-release tablets) and is a subsidiary of Nalpropion Pharmaceuticals LLC., which is headquartered in the United States of America (USA).

PASS Information

Title	Drug Utilisation and Safety Study of Mysimba/Contrave in			
Title	Europe and the United States			
Protocol version identifier	NB-451			
Date of last version of	August 7, 2023			
protocol	11ugust 7, 2025			
EU PAS register number	EUPAS103743			
Active substance	ATC code: A08AA62			
	Prolonged-release Mysimba/Contrave is a fixed-dose			
	combination of naltrexone hydrochloride [HCl] and			
	bupropion HCl			
Medicinal product	Mysimba®/Contrave® 8 mg/90 mg prolonged-release tablets			
Product reference	EU/1/14/988/001-002			
Procedure number	EMEA/H/C/003687/MEA/003.11			
Marketing authorisation	Orexigen Therapeutics Ireland Limited / Currax			
holder(s)	Pharmaceuticals, LLC			
Joint PASS	No			
Research question and	The primary objectives of the study are:			
objectives	 To describe demographic and baseline characteristics of patients initiating use of Mysimba/Contrave. To evaluate patterns of Mysimba/Contrave initiation and use, including estimating the number and percentage of patients compliant and non-compliant with the SmPC. 			
	 The secondary objectives of this study are: To assess and compare the observed incidence AESIs in usual clinical practice among users of Mysimba/Contrave compliant and non-compliant with the SmPC. To assess the proportions of patients in the following groups who are at increased risk for AESI and to describe the characteristics of the patients with AESI: a. Any user of Mysimba/Contrave; b. Users compliant with SmPC; and c. Users out of compliance with SmPC, as described above. 			
	 5. To assess the duration of Mysimba/Contrave use. 6. To identify to the extent possible within the data sources: Initial titration scheme and proportion aligned with SmPC; 			

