8. RESEARCH QUESTIONS AND OBJECTIVES

The aim of the study is to assess the long-term (548 days) real-world utilization patterns of Mysimba/Contrave use among patients who are prescribed Mysimba/Contrave. There are no a priori hypotheses for this study.

The primary objectives of the study are:

- To describe demographic and baseline characteristics of patients initiating use of Mysimba/Contrave; and
- 2. To evaluate patterns of Mysimba/Contrave initiation and use, including number of prescriptions, number of treatment episodes and duration between prescriptions, as well as estimating the number and percentage of patients compliant and non-compliant with the SmPC.

Analysis of compliance to the labelled indication and contraindications will be adapted to the specific SmPC for the country relevant to the data source (s). Examples of non-compliance include, but are not limited to:

Use inconsistent with labelled indication:

- 1. Age <18 years
- 2. Use other than management of weight
- 3. Management of weight in a patient who does not have obesity or is not overweight and has a weight-related comorbidity
- 4. A prescribed maintenance dose other than the Mysimba/Contrave 32mg/360mg
- 5. Continued use past 16 weeks without \geq 5% weight loss

Use in patients with contraindications:

- 6. A current diagnosis of uncontrolled hypertension, seizure disorder (or history of seizures), or end-stage renal failure
- 7. A history of bipolar disorder, anorexia nervosa or bulimia
- 8. A current dependence on chronic opioids or opiate agonists (e.g., methadone)
- 9. A current state of acute opiate withdrawal
- 10. Any concomitant treatment containing bupropion, naltrexone, or a MAOI
- 11. Patients with a known central nervous system tumour

Proprietary and Confidential:

- 12. Patients undergoing acute alcohol or benzodiazepine withdrawal
- 13. Patients with severe hepatic impairment (dependent on local SmPC)

The secondary objectives of this study are:

- 1. To assess and compare the observed incidence of AESIs in usual clinical practice among users of Mysimba/Contrave compliant and non-compliant with the SmPC. AESIs include new onset of the following:
 - 1. Seizures
 - 2. Suicidality (i.e., suicidal ideation, attempted suicide or completed suicide)
 - 3. Neuropsychiatric events (i.e., mania or depression)
 - 4. Hepatotoxicity
 - 5. Severe hypersensitivity reaction
 - 6. Serotonin syndrome

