9.7.4. Titration, Change in Dose, and Discontinuation

Among patients with available information, the proportion of patients with titration and dosing changes in alignment with the EU SmPC will be calculated. The local SmPC for the country of the data source may be used, if different than the EU SmPC.

Because reason discontinuation is rarely found in real world data, clinical events of interest and health status occurring within the 90-day window prior to discontinuation will be summarized for patients who discontinue treatment (i.e., do not refill their prescription). However, attribution to product is not possible.

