9.7.5. Missing Data

For each database, the number and proportion of patients with missing values for important variables (i.e., patient demographics, history, comorbidities and conditions, or medication) will be reported. If missing values occur in >5% of patients within a database, then each missing data element will be imputed based on the mode of each variable within strata defined by BMI category, age, and sex. In this DUS study, characteristics of individuals with missing information on BMI and weight will be described separately, along with correlates of this missing information. BMI and weight will not be imputed in the primary analysis. Imputed variables will not be used when determining *use inconsistent with labelled indication*.

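### Section 9.3.1.2 misstates the assumed dose as 128/360 mg per day instead of 32/360 mg, and should be reconciled with the rule on imputed values in 9.7.5

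*Protocol*

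**What the plan says.** Section 9.3.1.2 warns that "dose is unlikely to be available in Nordic data and sporadically available in US data". For patients without a listed dose it fixes a substitute: "4 pills per day with 32mg naltrexone and 90 mg bupropion in each pill) will be used as the dose for primary analyses". It adds that sensitivity analyses, described in 9.7.2, will assign other dosing to specific patient groups.

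The PASS Information table describes the product as "8 mg/90 mg prolonged-release tablets". Section 8, under primary objective 2, lists as an example of use inconsistent with the label "A prescribed maintenance dose other than the Mysimba/Contrave 32mg/360mg". Section 9.7.2 repeats this as item 4 of list (a), here called (a)4.

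Three other sections bear on the point:

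- Section 9.7.5 sets the missing-data rule. If more than 5% of patients in a database have missing values, "each missing data element will be imputed based on the mode of each variable within strata defined by BMI category, age, and sex". It then says: "Imputed variables will not be used when determining" use inconsistent with the labelled indication, which is the heading that contains (a)4.
- Section 9.7.4 limits the analysis of dosing changes: "Among patients with available information, the proportion of patients with titration and dosing changes in alignment with the EU SmPC will be calculated".
- Section 9.3.1.1 says that for Mysimba "the day's supply will be 28-days after titration".

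**The concern.** The assumed dose is an operative rule. By the protocol's own account it will apply to most or all Nordic patients and to many US patients. As printed, it contradicts both the tablet strength and the maintenance dose given elsewhere in the protocol. The sentence appears to combine the daily naltrexone total with the per-tablet bupropion strength.

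The second question is where the assumed dose is used. Section 9.3.1.2 does not limit it to duration and exposure, and (a)4 belongs to a primary objective. If an assumed dose decided (a)4, the assumption would fix the result and the data would play no part:

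- At the printed strength, every patient without a recorded dose would count as off-label on dose.
- At the intended strength, none of them could.

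Because (a)4 is one of the criteria that separate compliant from non-compliant users, the error could also reach the subgroup incidence rates in 9.7.3.1.

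**Working it through.** **Inputs.** Pills per day: 4 (9.3.1.2). Printed strength per pill: 32 mg naltrexone and 90 mg bupropion (9.3.1.2). Product strength: 8 mg/90 mg (PASS Information). Reference maintenance dose: 32/360 mg per day (sections 8 and 9.7.2). Tablets per dispensing: 112 (9.3.1.1, 9.7.2).

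**Daily dose** = pills per day × strength per pill.

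- As printed: 4 × 32 = 128 mg naltrexone; 4 × 90 = 360 mg bupropion.
- With the product strength: 4 × 8 = 32 mg naltrexone; 4 × 90 = 360 mg bupropion. This equals the reference dose.
- Back-check from the reference dose: 32/4 = 8 mg and 360/4 = 90 mg per pill.

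Only the naltrexone figure is wrong, by a factor of 128/32 = 4.

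**Effect on duration.** Days' supply = tablets / tablets per day.

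- After titration: 112/4 = 28 days, which agrees with 9.3.1.1.
- First dispensing with titration: 7 + 14 + 21 = 42 tablets over 21 days, then (112 − 42)/4 = 17.5 days, in total 38.5 days. This agrees with 9.7.2.

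Strength does not enter either formula, so the misprint leaves duration and person-time unchanged.

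**Effect on (a)4, only if the assumed dose (at the intended 32/360 mg) were used there.** Let m be the share of patients without a recorded dose and p the share off 32/360 mg among recorded doses. The reported share would be (1 − m)p instead of p, an understatement by a factor of 1/(1 − m).

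- No dose recorded (m = 1): 0 × p = 0, for example 0 of 3,000, where the correct entry is not assessable.
- The protocol gives neither m nor p for the US. For illustration:

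| Assumed m | Assumed p = 10% | Assumed p = 30% | Factor |
|---|---|---|---|
| 50% | 5% | 15% | 2 |
| 90% | 1% | 3% | 10 |

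**Does 9.7.5 close the route?** Most likely. Item (a)4 sits under the heading that 9.7.5 protects. Two things leave some doubt. The method in 9.7.5 is the mode within strata, triggered above 5% missing, whereas 9.3.1.2 sets one fixed value with no trigger. And 9.3.1.1 calls its filled-in days' supply imputed, while 9.3.1.2 calls its dose an assumption.

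**The case against.** The misprint cannot be disputed, but it can be called purely typographical, since no duration or rate changes. That is correct as to effect. It is still a wrong number in a rule that analysts are told to apply.

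The case against the second point is strong:

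- Section 9.7.5 bars imputed values from the very category that contains (a)4. A dose filled in because none was provided is an imputation in any ordinary sense.
- Section 9.3.1.1 uses the word imputed for a different rule (the mode by drug code), so the term is not confined to the strata of 9.7.5.
- Item (a)4 concerns a prescribed dose, and an assumed value is not a prescription.
- Section 9.3.1.2 stands under Exposure, and the sensitivity analyses that it points to concern supply and continued use. The likely intent is therefore a base case for exposure.
- Section 9.7.2 leaves the availability of variables to the SAP and says that missing categorical data will be counted.

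All of this stands. A reader might otherwise infer that the protocol has no safeguard, or that it plans to report 0% dose non-compliance in the Nordic databases. The documents support neither: 9.7.5 supplies a safeguard, and 9.4.1 says that Nordic dose adjustments are expected to be unavailable.

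What remains is a gap in wording. The rule for a missing dose is fixed in 9.3.1.2, for primary analyses without limit and with no reference to 9.7.5. Section 9.7.2 does not restrict the (a)4 denominator to recorded doses, as 9.7.4 does for dosing changes.

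**Conclusion.** Wrong as written, minor. The assumed daily dose in 9.3.1.2 is overstated fourfold for naltrexone (128 mg against 32 mg) and is correct for bupropion. This follows from the protocol's own figures and needs no assumption. Duration and person-time are unaffected.

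Section 9.7.5 most likely keeps the assumed dose out of (a)4, but 9.3.1.2 should say so. The 2- to 10-fold understatement is illustrative only: it rests on an assumed 50% to 90% of patients without a recorded dose, and arises only if 9.7.5 is not applied. It is not a forecast of what the study will report.

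**What to change.** In 9.3.1.2, change the naltrexone strength from 32 mg to 8 mg per pill, giving 32/360 mg per day. State there that the assumed dose serves only days' supply, duration and exposure, and that it counts as imputed under 9.7.5.

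In 9.7.2, report (a)4 only among patients with a recorded maintenance dose, show how many that is, and mark the rest as not assessable. Section 9.7.4 already limits dosing changes in this way.

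The cost is one corrected number and a sentence in each of the two sections. Duration results do not change. The downside is that there will be no Nordic figure for (a)4 where no dose is recorded, and that the US figure will rest on a smaller denominator.

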9.3.2. Outcomes

When available, the following variables will be collected after initiation of Mysimba/Contrave (Post-Index Date). A draft listing of variables available in each country is included in Appendix 3 and will be included as final in the Statistical Analysis Plan (SAP).

Proprietary and Confidential:

This document cannot be used, distributed, or reproduced in any way without the prior written consent of Currax Pharmaceuticals LLC.

- 1. BMI, height, and weight prior to index date, the date of initiation of the medication(s) of interest, (obtained directly from data sources; BMI may be calculated if height and weight available). In the event that BMI and/or weight are not available through licensed access to the Scandinavian National Patient Registries, an attempt will be made to identify the obese population through diagnosis codes or procedures such as counseling for weight loss. It should be noted that this approach may identify a more obese and more motivated population than what would be identified on the basis of BMI. In addition, an approach may be implemented to predict BMI or apply published algorithms predicting BMI. Details will be laid out in the SAP.
- 2. Weight will be obtained if available 16-24 weeks post-index date to evaluate use inconsistent with labelled indication. BMI after index date will be obtained in the same timeframe, if available.
- 3. Relevant comorbidities (obtained via ICD-10 codes):
 - 1. Weight-related comorbidities (i.e., type 2 diabetes, dyslipidaemia, hypertension)
 - 2. Neuropsychiatric conditions (mania, bipolar disorder, major depressive disorder [MDD], anorexia nervosa, bulimia)
 - 3. Uncontrolled hypertension
 - 4. Moderate or severe renal impairment
 - 5. End-stage renal disease
 - 6. Seizure disorder
 - 7. Hepatic impairment (defined by Child-Pugh score category)
 - 8. Central nervous system tumour
- 4. Concomitant medication use, including: naltrexone, bupropion, CYP2B6 inhibitors, CYP2B6 inducers, CYP2B6 substrates, CYP2D6 substrates, drugs that lower seizure threshold, opioid or opiate agonist, or MAOI (obtained via ATC [outpatient, Nordic data] or NDC [US data])
- 5. Pregnancy status and breastfeeding status (obtained via ICD-10 codes)
- 6. AESIs (obtained via ICD-10 codes):
 - 1. Seizures

- 2. Suicidality (i.e., suicidal ideation, attempted suicide or completed suicide)
- 3. Neuropsychiatric events (i.e., mania or depression)
- 4. Hepatotoxicity
- 5. Severe hypersensitivity reaction
- 6. Serotonin syndrome
- 7. Major adverse cardiovascular events (i.e., cardiovascular-related death, non-fatal myocardial infarction, or non-fatal stroke)

Deaths will also be described by treatment group, for those with vital status available.

- 7. Treatment discontinuation (assessed using ATC [outpatient, Nordic data] or NDC [US data])
- 8. Reason(s) for treatment discontinuation (obtained via ICD-10 codes in the 90 days prior to discontinuation)

All variables will be identified from the data sources via a pre-specified list of definitions (i.e., code lists; see Appendix 2). Occurrence of AESI based on diagnostic codes will be summarized for all patients, and for a subgroup of patients who do not adhere to conditions of the EU SmPC for the Scandinavian countries (adapted to local SmPC as needed) or to the FDA SmPC for the US. Such criteria include: not meeting appropriate criteria for the indication [obese (BMI \geq 30 kg/m²), or being overweight (BMI \geq 27 kg/m² to < 30 kg/m²) and having at least one weight-related co-morbidity (e.g., type 2 diabetes, controlled hypertension, or dyslipidemia) based on diagnostic codes. If BMI is not available, diagnostic and procedure codes for obesity and weight loss will be applied, recognizing that it will likely produce a more obese population than would be identified by BMI. Subgroup analyses will also be conducted to assess continuous treatment in patients with either renal or hepatic impairment.

Initiation of specific medications that could result with the occurrence of an event corresponding to an AESI (e.g., newly initiating anti-epileptic/seizure medication, newly initiating medications indicated for mania or depression) will also be tabulated. For hepatotoxicity, liver function tests can be used (when available) in addition to diagnostic codes.

For reason(s) patients who discontinue treatment (i.e., do not refill their prescription), events (potential AESIs and contraindications) and clinical status (magnitude of weight loss or gain)

Proprietary and Confidential:

occurring within the 90-day window prior to discontinuation will be summarized. It should be noted that weight may not be available in the Scandinavian registries.

To allow for multiple cycles of Mysimba/Contrave use and assessment of outcomes after initial exposure, the follow-up window for data collection after the index date will be up to 548 days (18 months), as an appropriate time-horizon for this specific purpose. All patient time during the follow-up window will be captured and censoring will occur at the earliest of death, disenrollment, 548 days of follow-up, or end of the study period (December 31, 2023).

